## 2.2 Secondary Objectives & Endpoints

- 2.2.1 To evaluate the safety of either Tremelimumab or MEDI4736 alone and in combination in patients with recurrent GBM. The endpoints will be the number, frequency, and severity of adverse events (as defined by the NCI Common Terminology Criteria for Adverse Events or CTCAE version 4.03).
- 2.2.2 To determine post-surgery, the time to progression(per Modified RANO criteria and iRANO criteria see below) for patients treated with either Tremelimumab or MEDI4736 alone and in combination of both, This will be defined as the number of months from the time of first dose of study treatment until progression of disease or death by any cause.
- 2.2.3 To determine post-surgery the overall survival for patients treated with Tremelimumab or MEDI4736 alone and in combination of both. This will be defined as the number of months surviving from the time of first dose of study treatment until death by any cause.
- 2.2.4 To assess post-surgery, MRI changes in patients treated with either Tremelimumab or MEDI4736 alone and in combination of both.

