#### 4.6 Duration of Follow Up

All subjects will be followed for survival for up to 2 years/24 months from stopping study treatment. Subjects who decline to return to the site for evaluations will be offered follow-up by phone every 8-16 weeks as an alternative.

Note that patients who discontinue treatment permanently for any reason other than progression will be followed for evidence of tumor response and disease status.

Any patient who withdraws their consent, will be considered as an early discontinuation, and may be replaced if this occurs before they have received the first dose of treatment. Patients who withdraw consent but receive at least one dose of treatment will be evaluable for toxicity even if they are not fully evaluable for response. The accrual goal has been set to allow up to 45 patients to be enrolled in order to allow for early discontinuations.

If a patient withdraws consent, no further treatment or study-specific testing will be completed. The primary reason for a patient's withdrawal from the study is to be recorded in the source documents. All patients will be followed until death or 2 years/24 months from stopping treatment.

Subjects who are permanently discontinued from further receipt of investigational product, regardless of the reason (withdrawal of consent, due to an AE, other), will be identified as having permanently discontinued treatment.

Subjects who are permanently discontinued from receiving investigational product will be followed for safety for 30 days post last-dose visit including the collection of any protocol-specified blood specimens, unless consent is withdrawn or the subject is lost to follow-up or enrolled in another clinical study. If a subject is enrolled in another clinical study, they will be followed until all AEs are resolved or stable. If enrolled onto another clinical study, it is not necessary to follow the subject for survival or progression.

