#### 4.8 Patient Replacement/ Addition

- Any patient who is consented but does not receive at least one dose of investigational drug will be replaced.
- Any patient who withdraws their consent or otherwise discontinues study for any reason prior to undergoing surgery, will be considered as an early discontinuation, and another patient may be added as necessary.

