-  During adjuvant treatment, one cycle is defined as 4 weeks for patients on Arms 1 and 2. For patients on Arm 3, please refer to the schedule outlined in footnote #14.
-  Blood samples will be collected for various research tests at 1 st pre-operative treatment, day of surgery, C1D1 and at each adjuvant treatment imaging visits (i.e. every 2 cycles or 8 weeks):
  - a) 10ml blood in one 10ml Sodium heparin tube: To be collected and processed by the [name] lab for peripheral blood lymphocytes (PBLs).
  - b) 8m (2x4ml) blood in two 5ml EDTA (purple top) tubes: To be collected and processed by the [name] lab for gene expression profile using mononuclear cells.
  - c) 10ml blood in one 10ml red top tube: To be collected and processed by the [name] lab for analysis of tryptophan catabolites and cytokines.
  - Please refer to section 9.0 and laboratory manual for more details
-  Any patient who undergoes further surgery will have the option to use their tumor tissue for research to understand the immunologic changes occurring at the time of presumed drug failure. Please refer to Section 9 and laboratory manual for details.
-  Follow up for disease progression (if not already documented) and survival will occur every 8-16 weeks once off treatment. All patients will be followed until death or 2 years/24 months from stopping treatment.
-  Patients enrolled on Arm 1 will receive tremelimumab monotherapy: one 75 mg dose IV on day 1 (+/- 2 days) per cycle (every 4 weeks) up to 24 months.
-  Patients enrolled on Arm 2 will receive MEDI4736 monotherapy: one 750 mg dose IV on days 1 and 15 (+/- 2 days allowed for each) per cycle (every 2 weeks) up to 24 months.
-  Patients enrolled on Arm 3 will receive combination therapy (tremelimumab 75 mg + MEDI4736 750 mg) according to the following schedule: Tremelimumab will be administered IV every 4 weeks (Day 1 of each cycle) and MEDI4736 750mg every 2 weeks (Day 1 and Day 15 of each cycle) until the patients have received 7 doses of Tremelimumab and 14 doses of MEDI4736. Thereafter, from Cycle 7 (Week 25), Tremelimumab will be given every 12 weeks (+/-7 days) and MEDI4736 will be given every 2 weeks (+/- 2 days) until permanent discontinuation criteria (e.g. disease progression) is met. If there is no progression of disease, they will continue on treatment for up to 24 months.

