### 6.2 Secondary Endpoints

- 1. To evaluate the safety of either Tremelimumab or MEDI4736 alone and in combination for patients with recurrent GBM. The endpoints will be the number, frequency, and severity of adverse events (as defined by the NCI Common Terminology Criteria for Adverse Events or CTCAE version 4.03). Only patients who have been administered at least one dose of investigational drug will be evaluable for this endpoint.
- 2. To determine post-surgery, the time to progression (per Modified RANO criteria and iRANO criteria see below) for patients treated with either Tremelimumab or MEDI4736 alone and in combination of both. This will be defined as the number of months from the time of first dose of study treatment until progression of disease or death by any cause. Only patients who have been administered at least one dose of investigational drug and undergone surgery will be evaluable for this endpoint.
- 3. To determine post-surgery the overall survival for patients treated with Tremelimumab or MEDI4736 alone and in combination of both. This will be defined as the number of months surviving from the time of first dose of study treatment until death by any cause. Only patients who have been administered at least one dose of investigational drug and undergone surgery will be evaluable for this endpoint.
- 4. To assess post-surgery, the MRI changes in patients treated with either Tremelimumab or MEDI4736 alone and in combination of both. Only patients who have been administered at least one dose of investigational drug, undergone surgery, and have undergone at least one post-surgery disease assessment will be evaluable for this endpoint.

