#### 7.3 Adverse Event Reporting 7.3.1 Routine Reporting

Adverse events will be recorded using a recognized medical term or diagnosis that accurately reflects the event. Adverse events will be assessed by the investigator for severity, relationship to the investigational product, possible etiologies, and whether the event meets criteria of an SAE and therefore requires immediate notification to the QAM and AstraZeneca/MedImmune Patient Safety.

The following variables will be collected for each AE:

- AE (verbatim)
- The date when the AE started and stopped
- Changes in NCI CTCAE grade and the maximum CTC grade attained
- Whether the AE is serious or not

In addition, the following variables will be collected for SAEs as applicable:

• Date AE met criteria for serious AE

- Date Investigator became aware of serious AE
- AE is serious due to
- Date of hospitalization
- Date of discharge
- Probable cause of death
- Date of death
- Autopsy performed
- Description of AE
- Causality assessment in relation to Study procedure(s)

All routine adverse events, such as those that are expected, or are unlikely or definitely not related to study participation, are to be reported on the appropriate eCRF. Routine AEs will be reviewed by the Data and Safety Monitoring Committee (DSMC) according to the study's phase and risk level, as outlined in the DSMP.

Adverse events and serious adverse events will be recorded from time of signature of informed consent, throughout the treatment period and including the follow-up period (90 days after the last dose of MEDI4736 or tremelimumab or the combination of both). During the course of the study all AEs and SAEs should be proactively followed up for each subject. Every effort should be made to obtain a resolution for all events, even if the events continue after discontinuation/study completion.

If a subject discontinues from treatment for reasons other than disease progression, and therefore continues to have tumor assessments, drug or procedure-related SAEs must be captured until the patient is considered to have confirmed PD and will have no further tumor assessments.

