**Time to Progression:** From date of first treatment to the date of first observation of definitive progressive disease, non-reversible neurologic progression or increasing steroid requirements (applies to stable disease only), death due to any cause, or early discontinuation of treatment. Patients not reaching the progression endpoint at last follow-up will be censored at that time.

**Time to Death**: From date of first treatment to date of death due to any cause. Patients alive at last follow-up will be censored at that time.

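### Section 10.3 scores early discontinuation of treatment as a time-to-progression event, while sections 2.2.2 and 6.2 count only progression or death

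*Combined protocol and SAP*

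**What the plan says.** Section 10.3 holds the only operational event and censoring rule for time to progression. The clock starts at first treatment. It stops at definitive progressive disease, at irreversible neurologic decline or rising steroid need (flagged as applying to stable disease), or at "death due to any cause, or early discontinuation of treatment". Patients who have reached none of these are censored at last follow-up.

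Sections 2.2.2 and 6.2 define the endpoint from first dose "until progression of disease or death by any cause". Section 6.2 adds: "Only patients who have been administered at least one dose of investigational drug and undergone surgery will be evaluable for this endpoint".

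Three places govern what happens after a stop without progression:

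- Section 4.6: "patients who discontinue treatment permanently for any reason other than progression will be followed for evidence of tumor response and disease status".
- Section 5.2, footnote 11: "Follow up for disease progression (if not already documented) and survival will occur every 8-16 weeks once off treatment".
- Section 7.3.1 takes continued assessment for granted: "If a subject discontinues from treatment for reasons other than disease progression, and therefore continues to have tumor assessments".

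The term also appears in two other places. Section 4.6 says "Any patient who withdraws their consent, will be considered as an early discontinuation". Section 4.8 uses it for patients who leave the study "prior to undergoing surgery, will be considered as an early discontinuation".

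**The concern.** One secondary endpoint has two event lists. A patient who stops drug without progressing has an event under 10.3 and is still at risk under 2.2.2 and 6.2. An analyst working from the statistics section would apply 10.3, and progression data collected after the stop could then not change the result.

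Such stops are built into the design. Section 4.4 orders permanent discontinuation for several toxicities, Grade 3 or 4 pneumonitis among them. Section 4.5 adds long toxicity delays, intercurrent illness and investigator decision. If these count as events, the curve mixes tolerability with tumor control.

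The outcome is also used downstream. Section 9.2 separates responders from non-responders, if they can be separated, by progression-free and/or overall survival. Section 10.3 relates T-cell and PD-L1 changes to survival outcomes by Cox regression, without saying whether time to progression is one of them. A patient with strong immune activation who stops for an immune event could be filed as an early failure, which works against the aim of linking immune change to outcome.

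**Working it through.** The plan gives no event count, hazard ratio or power for time to progression, so there is no stated figure to reproduce. The main check compares the texts.

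**1. Event lists.** Sections 2.2.2 and 6.2: progression; death from any cause. Section 10.3: progression; irreversible neurologic decline or rising steroid need; death from any cause; early discontinuation of treatment. The start point is the same in all three.

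**2. Event or censoring?** 10.3 censors only patients who have not reached the endpoint by last follow-up. Discontinuation stands in the list that ends the interval, so it reads as an event.

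**3. Follow-up.** 4.6, footnote 11 of 5.2 and 7.3.1 continue disease follow-up after a stop without progression. This fits 2.2.2 and 6.2. The exceptions are consent withdrawal (4.6, 4.7), loss to follow-up, and enrolment on another study (4.6).

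**4. Possible meanings of the clause.**

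- Any stop of study drug: toxicity stops become events. This conflicts with 2.2.2 and 6.2.
- Consent withdrawal, as in 4.6: not an event in 2.2.2 or 6.2, so the conflict remains.
- Leaving before surgery, as in 4.8: 6.2 excludes these patients from the endpoint, so the clause would apply to nobody in the analysis.

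No reading makes the sections agree.

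**5. Size, as illustration.** Assume constant, independent hazards: a for progression or death, b for a stop without progression. The share whose first 10.3 event is such a stop is p = b/(a + b).

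- Median under 2.2.2 and 6.2: ln 2 / a.
- Median under 10.3: ln 2 / (a + b) = (1 − p) × ln 2 / a.
- The median is therefore shortened by the fraction p.

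The documents give no p for glioblastoma. Over an assumed range:

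- p = 10%: factor 0.90. An assumed true median of 3 months reads 3 × 0.90 = 2.7 months.
- p = 20%: factor 0.80; 3 × 0.80 = 2.4 months.
- p = 30%: factor 0.70; 3 × 0.70 = 2.1 months.

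At p = 10%, with patients independent, the chance of at least one affected patient is 1 − 0.9^10 = 65% in an arm of 10 and 1 − 0.9^15 = 79% in an arm of 15.

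**6. What deletion alone leaves.** The steroid and neurologic items remain in 10.3. Section 6.4 accepts clinical deterioration without another explanation as progression, which overlaps with the neurologic item. It does not make a steroid increase by itself progression, and the RANO table marks corticosteroids as not applicable for progressive disease.

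**The case against.** The strongest reply is about terminology. For patients who come off drug because of an adverse event, the protocol speaks of permanent discontinuation (4.4, 4.6). It keeps early discontinuation for consent withdrawal and for leaving before surgery. On that usage a pneumonitis stop is not an event, and both the toxicity harm and its share of the illustration disappear. This stands as a possible reading. It does not settle the matter, because 10.3 speaks of discontinuing treatment, which is broader, and because the narrower meanings still do not fit 2.2.2 and 6.2 (step 4).

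A second reply is that follow-up off treatment is thinner than the text suggests. Footnote 11 sets an interval of 8 to 16 weeks and 4.6 allows telephone contact. The 5.2 table schedules no imaging after the discontinuation visit, and its follow-up column marks only survival status. Censoring some of these patients may therefore be informative. This also stands. It is a reason to state the censoring rule clearly, not a reason to score the stop as progression.

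A reader might also want to attach a number from the background data: section 1.4.2 reports that 27 of 102 patients (26.5%) stopped the combination for adverse events. The documents do not support using it as p or as a bound on p. It counts adverse-event stops only, omits voluntary withdrawal and investigator decisions, and may include stops after progression. It comes from lung cancer at one data cut, with some cohorts at higher tremelimumab doses. Nor can it be set against the figures in 1.3.3 for MEDI4736 alone to predict a gap between arms. Those list only adverse events that led to a stop in at least two subjects, while the 26.5% covers all adverse-event stops.

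**Conclusion.** The inconsistency is real and sits in current text. 10.3 should be corrected, because its event list cannot be squared with 2.2.2 and 6.2 on any reading, and the follow-up rules side with 2.2.2 and 6.2. On the literal reading, time to progression is biased downward. The size is the unknown share p of patients whose first event is a stop without progression, given constant independent hazards; a range of 10% to 30% is an assumption, not an estimate. Misfiling in the 9.2 responder split follows on the same reading. An effect on the Cox analysis is possible only if its survival outcomes include this endpoint.

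A reader might infer that the trial's main conclusions or its comparison of arms are compromised. The documents do not support that. The endpoint is secondary and unpowered, is summarized by Kaplan-Meier curves, and has no planned between-arm test. The primary T-cell endpoint and overall survival do not use this definition.

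**What to change.** In the time-to-progression definition of 10.3, strike early discontinuation from the event list, leaving progression and death from any cause. Add one sentence: patients without progression or death, including those who withdraw consent, are lost to follow-up or join another study, are censored at their last disease assessment. The present rule censors at last follow-up, so a telephone survival contact could extend progression-free time past the last date on which disease was assessed.

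These two edits remove the discontinuation mismatch only. In the same revision, reconcile the steroid and neurologic items in 10.3 with the progression criteria in 6.4, either by dropping them or by stating there when they count.

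If the investigators want a measure that includes treatment stops, report time to treatment failure separately under that name.

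The cost is a few lines of text. No new samples or patients are needed, and 4.6 and footnote 11 already call for disease follow-up. The small downside is possible informative censoring, given the thinner follow-up off treatment. Reporting the number censored and the reasons by arm would let readers judge it.

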Research blood 	X		X 			
Survival status						X

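### Time to progression has two conflicting event definitions, and its censoring date need not be a disease assessment

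*Combined protocol and SAP*

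**What the plan says.** **Events.** Sections 2.2.2 and 6.2 (item 2) run the endpoint from first dose "until progression of disease or death by any cause". The Time to Progression paragraph of 10.3 gives a longer list, which closes with "death due to any cause, or early discontinuation of treatment". The same section elsewhere calls the endpoint progression-free survival and assigns it to Kaplan-Meier curves.

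**Censoring.** The only rule in the plan is in 10.3: "Patients not reaching the progression endpoint at last follow-up will be censored at that time". The rule for time to death also uses last follow-up.

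**Follow-up after treatment.** Section 4.6 says patients who stop permanently for reasons other than progression "will be followed for evidence of tumor response and disease status". It also says: "Subjects who decline to return to the site for evaluations will be offered follow-up by phone every 8-16 weeks as an alternative". Footnote 11 of the 5.2 schedule states: "Follow up for disease progression (if not already documented) and survival will occur every 8-16 weeks once off treatment". In that schedule tumour imaging is marked at Cycle 1, at Cycle 3 onward and at treatment discontinuation. The only row marked in the Follow-up column is "Survival status".

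**The concern.** Last follow-up is a sound censoring date for survival, because any contact shows whether the patient is alive. It is not sound for progression, because a phone call cannot show that a scan would have been clear. A patient without a recorded event is credited with progression-free time up to a contact at which progression may not have been assessed.

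Whether this matters depends on what happens to a patient who stops drug without progression, and on that the plan contradicts itself. Under 10.3 the patient has had an event. Under 2.2.2 and 6.2 the patient is still at risk, and 10.3 supplies the only censoring date. The two readings bias the Kaplan-Meier curve in opposite directions. They also feed different outcomes into the Cox analyses if PFS is among the survival outcomes used there. With 10 to 15 patients per arm, a few such patients can visibly move a curve.

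**Working it through.** The plan states no median PFS, event count or rate of loss of imaging, so there is no figure of its own to reproduce.

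**1. The readings side by side, for a patient who stops for toxicity without progression and has no later scan**

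- 10.3 as written: event on the day of stopping. PFS is too low.
- 2.2.2/6.2 events with 10.3 censoring: at risk until death, or censored at the last contact. PFS is too high.
- Under 10.3 alone the censoring date matters only for patients who complete 24 months and then decline visits, or who miss scans on treatment. In the simulation below, 0% to 5% were still on treatment and progression-free at 24 months.

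**2. Illustration. All inputs are assumptions except the 8-week scan interval (5.2) and the 24 months of follow-up after stopping (4.6)**

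Progression is exponential with a median of 4 months, and the median from progression to death is 6 months. Stopping is exponential, with 10%, 20% or 30% stopping before progression and having no later scan (200,000 simulated patients per setting).

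Scan interval: 8/4.345 = 1.84 months, so the last scan before month 6 is at 5.52 months.

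- Scans continue: 0.5^(5.52/4) = 38.4%.
- 10.3 events: λp = ln2/4 = 0.1733 and λd = λp·f/(1−f), which is 0.0193 at f = 10% and 0.0743 at f = 30%. PFS at 6 months ≈ exp[−(λp+λd)·5.52]·exp[−λd·0.48]. This gives 0.345 × 0.991 = 34% at 10%, and 0.255 × 0.965 = 25% at 30%.

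Simulated 6-month PFS:

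| Stopping without progression | 10% | 20% | 30% |
|---|---|---|---|
| Scans continue | 38.3% | 38.3% | 38.2% |
| 10.3 events | 34.2% | 29.5% | 24.5% |
| 2.2.2/6.2 events, no later scans | 40.3% | 42.7% | 45.2% |
| All stoppers censored at last scan | 37.3% | 35.9% | 34.1% |

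Here the overstatement is +2 to +7 points and the understatement −4 to −14. Over the full grid (median progression 2, 4 or 6 months; 4 or 6 months from progression to death) the overstatement runs from +1 (52.8% to 53.7%) to +14 (14.8% to 28.8%). The understatement runs from −3 to −14.

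A second model gives +5 to +10 points. It assumes median PFS of 2 to 4 months, median post-progression survival of 5 months, and 20% to 40% ending imaging between months 1 and 4. At 3 months and 26.5%, it gives 25% true against 31% recorded.

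**3. What last-assessment censoring achieves**

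The last row of the table is 1 to 4 points below the continued-scan value: close, not equal. It censors every stopper at the last scan, including those who die later. A rule that moves only patients without progression or death leaves later deaths as events on the date of death. With λs = ln2/6 = 0.1155, the share of stoppers alive 24 months after stopping is (λp·0.5^4 − λs·0.5^6)/(λp − λs) = (0.01083 − 0.00180)/0.0578 = 0.156. So 84% have died and are still carried progression-free to death. Rerunning the table's model (400,000 patients per setting) gives 40% to 44% under that rule alone. Also censoring deaths after two or more missed scans gives 37% to 34%.

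**The case against.** **A reader might infer that 10.3 as written overstates PFS.** It does not. Its own list makes early discontinuation an event, which pushes the estimate down. Overstatement needs the 2.2.2/6.2 events together with 10.3's censoring date, and no single section contains that combination. This objection stands against any claim resting on 10.3 alone. It does not remove the problem: 2.2.2 and 6.2 state the endpoint and have no censoring rule but 10.3's. Correcting the event list without the censoring date would exchange an understatement for an overstatement.

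**A reader might also infer that patients who stop are then only phoned.** The plan intends otherwise. Section 4.6 and footnote 11 continue disease follow-up, 7.3.1 presumes that tumour assessments go on after a stop without progression, and phone contact is an alternative for those who decline visits. Section 6.4 also lets clinical deterioration establish progression without a scan. All of this stands and makes the simulated overstatement an upper case. What is missing is any imaging type or interval after treatment.

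**Nor do the documents support a bias towards the combination arm.** Under 10.3 more toxicity stops mean more events. The 26.5% (27/102) in section 1.4.2 is discontinuation for adverse events in lung cancer patients on the combination. It is not a rate of lost imaging in glioblastoma.

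**The scale is modest.** At 15 per arm and 25% PFS, the 95% half-width is 1.96·√(0.25·0.75/15) = 22 points, larger than the bias. That lowers the priority, but bias does not shrink with more patients and a wording change removes the contradiction.

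**Conclusion.** The concern holds in this form: the endpoint has two incompatible event definitions, and its only censoring rule is not tied to a disease assessment. The direction of bias depends on the definition used: down under 10.3, up under 2.2.2/6.2 with 10.3's censoring.

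The size cannot be derived from the documents. The central range of +2 to +10 points at 6 months rests on assumed exponential times, assumed stopping rates and no scans after stopping. The extremes (+1 and +14) come from the slowest-progression, least-stopping and fastest-progression, most-stopping settings.

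This should be fixed but is not critical. The endpoint is secondary, described by Kaplan-Meier curves and possibly used in Cox correlations, with no planned between-arm test of PFS. The primary endpoint, sample size and Type I error rate are unaffected.

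**What to change.** 1. **One event definition in 2.2.2, 6.2 and 10.3:** time from first dose to progression or death from any cause. Remove early discontinuation of treatment as an event, and use the name progression-free survival throughout.
2. **Censoring in 10.3:** patients without progression or death are censored at their last adequate disease assessment. Phone contacts count for overall survival only.
3. **Sensitivity analysis:** deaths after two or more missed assessments are censored at the last adequate assessment. This is needed because item 2 alone leaves those patients progression-free until death.
4. **Schedule:** state in 5.2 whether, and at what interval, patients who stop without progression are imaged. Otherwise a missed assessment is undefined off treatment.

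The cost is a few sentences and one extra analysis. It needs the dates of disease assessments, and items 1 to 3 require no new patient procedures. The downside is slightly shorter censored follow-up and a slightly less favourable PFS than the 2.2.2/6.2 reading would give. Compared with 10.3 as written, removing discontinuation as an event raises the estimate. Last-assessment censoring that also sets aside late deaths comes close to the continued-scan value but does not reproduce it.
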